7.2. Rationale and Discussion of Study Design

The present study employs a randomized, double-blind, placebo-controlled, parallel design, which is generally considered to be the gold-standard for clinical trials. The use of a placebo for the study comparator is based on the absence of an active comparator that could be delivered by the i.n. route, which is essential for maintaining the study blind.

Subjects will complete the HAM-A, an established scale, to rate their anxiety. Additional evaluations include the PGI-C, ADNM (a newer scale validated for classification of severity of AjDA), and the IADQ (a recently validated questionnaire to identify stressful events subjects have experienced, as well as their potential social impact). Objective evaluations, performed by the Investigator and a trained observer, include the CGI-I and CGI-S.

Safety assessments are standard for the evaluation of an investigational medicinal product, and include collection of AEs and SAEs, and evaluation of vital signs, safety laboratory tests, ECGs, and physical examinations; given the use of the i.n. route of administration, the physical examination will include an examination of the nasal passages. Given that subjects are patients with a confirmed diagnosis of AjDA, the C-SSRS will be used at each study visit as a precautionary measure.

7.3. Selection of Doses in the Study

The i.n. route of administration is required for the small quantities of PH94B to engage directly with nasal chemosensory neurons interspersed in the nasal olfactory epithelium.

Nonclinical and clinical studies with PH94B are summarized in the IB. Nonclinical and clinical data have shown that PH94B is safe for use in human subjects at increasing doses up to [REDACTED]. PH94B could not be quantified in blood samples of human subjects administered [REDACTED] i.n. in a Phase 1 trial. No SAEs associated with the administration of PH94B have been observed in any clinical study to date. To date, the safety margin-based No-Observed-Adverse-effect level from toxicity levels have indicated that the proposed doses are safe. The profile of physiological and behavioral responses to PH94B was similar for males and females, but the magnitude of effect is slightly reduced for males at the 1.6 μ g dose. This study proposes that [REDACTED] of PH94B or placebo [REDACTED], be self-administered i.n. by the subjects 4 times per day, separated by at least 2 hours (target morning, noon, early evening, and bedtime). This is based on Phase 1 and Phase 2 study outcomes in general, and in particular on the observations made in study PH94B-CL019. Subjects will be randomly assigned to treatment with either PH94B or placebo.

7.4. Study Sites

It is projected that up to 2 centers will participate.

7.5. End of Study Definition

A clinical trial is considered completed when the last subject's last study visit has occurred.

8. SUBJECT POPULATION

8.1. Selection of Study Population

Eligibility for participation in the study will be determined from demographic information, medical and psychiatric history, physical and psychiatric examination, ECG, clinical laboratory findings, and clinical rating scale assessments performed at the Screening (Visit 1) and Baseline (Visit 2). Subjects may be recruited from the Investigator or sub-Investigator clinical practices, the center's existing database, referring physicians, or direct advertisement or other lead generation source. Any information to be disseminated to potential subjects (handouts, brochures, etc.), as well as direct advertisements, including direct electronic or digital advertising, must be approved by VistaGen Therapeutics, Inc. and by the central IRB prior to use and implementation.

8.2. Study Entry Criteria

Subjects who do not meet all of the eligibility criteria will not be enrolled.

8.2.1 Inclusion Criteria

To be considered eligible to participate in the study, a subject must meet the inclusion criteria listed below:

1. Written informed consent provided prior to conducting any study-specific assessment.
2. Male and female adults, ≥ 18 years of age.
3. Current diagnosis of AjDA as defined in the DSM-5.
4. Clinician-rated HAM-A score ≥ 20 at Screening (Visit 1) and no greater than 15% decrease at Baseline (Visit 2).
5. Clinician-rated MADRS total score < 20 at Screening (Visit 1) and Baseline (Visit 2).
6. Clinical Global Impression - Severity Scale score ≥ 4 at Screening (Visit 1) and Baseline (Visit 2).
7. Women of childbearing potential must be able to commit to the consistent and correct use of an effective method of birth control throughout the study and must also have a negative urine pregnancy test result at both Screening (Visit 1) and Baseline (Visit 2), prior to IP administration. Effective methods of contraception include condoms with spermicide, diaphragm with spermicide, hormonal contraceptive agents (oral, transdermal, or injectable), or implantable contraceptive devices.
8. Males whose sexual partners are women of childbearing potential must commit to the consistent and correct use of an effective method of birth control throughout the study.
9. Negative COVID-19 test for subjects with COVID-19 symptoms or who have had direct exposure to someone with a positive COVID-19 test, as determined by the Investigator.

8.2.2 Exclusion Criteria

To be considered eligible for entry into the study, a subject must not meet any of the following exclusion criteria:

1. Any history of schizophrenia or schizoaffective disorder.

2. Any other current Axis I disorder, including, but not limited to, major depressive disorder, bipolar disorder, post-traumatic stress disorder, obsessive-compulsive disorder, premenstrual dysphoric disorder, and generalized anxiety disorder, which is in poor control and the primary focus of treatment.
3. A diagnosis of SAD.
4. A score >60 on the Liebowitz Social Anxiety Scale (LSAS).
5. Subjects who meet criteria for moderate or severe alcohol or substance use disorder within 1 year prior to study entry.
6. In the opinion of the Investigator, the subject has a significant risk for suicidal behavior during their participation in the study, or
 - a. At Screening (Visit 1): the subject scores “yes” on items 4 or 5 in the Suicidal Ideation section of the C-SSRS with reference to a 6-month period prior to screening; or
 - b. At Screening (Visit 1): the subject has had one or more suicidal attempts with reference to a 2 year period prior to screening; or
 - c. At Baseline (Visit 2): the subject scores “yes” on items 4 or 5 in the Suicidal Ideation section of the C-SSRS with reference to screening; or
 - d. The subject is considered to be an imminent danger to themselves or others.
7. Clinically significant nasal pathology or history of significant nasal trauma, nasal surgery, total anosmia, or nasal septum perforation that may have damaged the nasal chemosensory epithelium.
8. An acute or chronic condition, including an infectious illness, uncontrolled seasonal allergies at the time of the study, or significant nasal congestion that potentially could affect drug delivery to the nasal chemosensory epithelium. The Investigator may allow concomitant use of over-the-counter nasal decongestants as needed, since there is no apparent drug interaction between these and PH94B.
9. Concomitant use of any anxiolytics, such as benzodiazepines, buspirone, or cannabinoids during the study and within 30 days of Baseline (Visit 2).
10. Concomitant use of any over-the-counter, prescription product, or herbal preparation for treatment of the symptoms of anxiety during the study and within 30 days before study entry. Selective serotonin reuptake inhibitors, serotonin-norepinephrine reuptake inhibitors, or other approved antidepressants are permitted if the dose has been stable for 30 days prior to Baseline (Visit 2).
11. Women who have a positive urine pregnancy test prior to IP administration or are currently breast feeding.
12. Subjects with clinically significant abnormalities in hematology, blood chemistry, urinalysis, electrocardiogram, or physical examination identified at Screening(Visit 1) that in the clinical judgment of the Investigator, could place the subject at undue risk, interfere with study participation, or confound the results of the study.
13. Subjects with a positive urine drug screen at either Screening(Visit 1) or Baseline(Visit 2).

14. Any current clinically significant and/or uncontrolled medical condition, based on medical history or as evidenced in screening assessments, such as COVID 19, HIV, cancer, stroke, congestive heart failure, uncontrolled diabetes mellitus, or any other medical condition or disease that, in the clinical judgment of the Investigator, could place the subject at undue risk, interfere with study participation, or confound the results of the study.
15. Use of a concomitant medication that, in the clinical judgment of the Investigator, could place the subject at undue risk, interfere with study participation, or confound the results of the study.
16. History of cancer or malignant tumor not in remission for at least 2 years. Basal cell skin cancers are not exclusionary.

8.3. Premature Subject Withdrawal

All subjects will be advised that they are free to withdraw from participation in this study at any time, for any reason, and without prejudice. The Investigator should make every reasonable attempt to complete all of the scheduled weekly assessments; with the exception of subjects who withdraw consent to participate in the study. Investigators must attempt to contact subjects who fail to attend scheduled visits by telephone or other means to exclude the possibility of an AE being the cause of withdrawal. Should this be the cause, the AE must be documented, reported, and followed as described in Section [11.2](#).

The sponsor reserves the right to request the withdrawal of a subject due to protocol deviations or other reasons.

The Investigator also has the right to withdraw subjects from the study at any time for the following reasons:

- Any AE, laboratory abnormality, or concomitant illness which, in the opinion of the Investigator, indicates that continued treatment with IP or any other aspect of the study is not in the best interest of the subject
- Disease progression that, in the Investigator's opinion, precludes the subject's continued participation in the study
- Significant non-compliance with the requirements of the protocol or treatment
- The subject misses ≥ 2 consecutive scheduled visits during the 4-week treatment period
- The subject is unable to tolerate study medication based on the Investigator's judgment
- Subject requires PH94B administration more than 4 times per day
- The subject requires a medication prohibited by the protocol (Section [9.7.2](#))
- Termination of the study by VistaGen Therapeutics, Inc.
- At the discretion of the Investigator or VistaGen Therapeutics, Inc.

If a subject is withdrawn before completing the study, the reason for withdrawal and the date of discontinuation will be recorded on the appropriate page of the electronic case report form (eCRF). Whenever possible and reasonable, the evaluations that were to be conducted at the completion of the study should be performed at the time of premature discontinuation.

Subjects who discontinue early from the study will be asked to return for originally scheduled weekly assessments. If this is not possible, all attempts will be made to have subjects return to the study center to complete the assessments listed for Visit 6 (see Section 10.2.4) as soon as possible. All attempts, including phone or email, to contact the subject must be recorded in the source documents. If the subject fails to respond to those methods, a certified, return receipt letter must be sent to the subject's address indicating that they should contact the study center, with a copy retained in the source documents. Only if all of these attempts fail will it be deemed that the subject is in fact Lost to Follow-up and no final safety data can be collected. No tapering of IP is required in the event of early withdrawal.

Subjects who sign the informed consent form (ICF) and are subsequently withdrawn will not be replaced.

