6.1.4. Handling of Dropouts or Missing Data

Data will be included in the analysis according to the analysis visit windows described in Section 6.1.5.

Treatment of intercurrent events (ICEs) will be as described in Table 3. Briefly, subjects who withdraw from the study after treatment begins will be encouraged to complete an Early Termination Visit where all Visit 6 assessments will be performed. If the subject is lost to follow-up or otherwise unable to complete the Visit 6 assessments or if the subject uses a prohibited medication prior to the planned end of treatment, the Visit 6 HAM-A score will be set to missing. If the fraction of missing change from baseline to Visit 6 HAM-A total scores in the ITT population is ≤ 0.05 , missing change scores will be imputed with treatment group mean change scores for the primary efficacy analysis. If the fraction of missing change scores is greater than 0.05, multiple imputation of the change from baseline to Visit 6 HAM-A total scores will be carried out for the primary efficacy analysis. The fraction of missing change from baseline to Visit 6 HAM-A total scores will be computed as described in Section 6.1.7.2. The multiple imputation procedure will not impute individual HAM-A item scores or HAM-A total scores; only change from baseline to Visit 6 HAM-A total scores will be imputed. Other efficacy and safety data will not be imputed and will be analyzed as observed.

Table 3: Strategies for Intercurrent Events

ICE	Strategy for Addressing ICE
Treatment discontinuation following randomization but prior to Week 4.	While on Treatment Strategy The research objectives seek to understand the response to PH94B compared to placebo while subjects are actively using the study medication. Subjects who discontinue will undergo an Early Termination Visit and provide all Visit 6 outcome measures and safety assessments for the efficacy analysis.

ICE	Strategy for Addressing ICE

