6.1.5. Analysis Visit Windows

Efficacy data will not be windowed and will be analyzed as per the nominal visit present in the database. Efficacy data includes scores on HAM-A, CGI-I, PGI-C, ADN, and IADQ. As described in the Protocol, a ± 2 -day window will be allowed for each visit following Baseline (Visit 2). If a subject attends a visit outside of the window specified in the Protocol, this will be considered an out-of-window visit protocol deviation. Subjects who come in for a visit later than the 2-day window specified in the Protocol, who may have missed days of taking the IP, will be assessed on a case-by-case basis to determine whether they will be included in the analysis. Safety and baseline medical or psychiatric data will not be windowed and will be analyzed as per the nominal visit present in the database. These data include physical examinations, vital signs, clinical laboratory tests, ECGs, adverse events, prior and concomitant medications, and data from the MINI, MADRS, PWC-20, C-SSRS, LSAS, and CGI-S. Unscheduled assessments of safety parameters will be included in listings only.

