8.1. Primary Efficacy Analysis

The primary endpoint will be tested for the following hypothesis:

H₁₀: Mean change in HAM-A total score from Visit 2 (Baseline) to Visit 6 does not differ between PH94B and placebo.

H₁₁: Mean change in HAM-A total score from Visit 2 (Baseline) to Visit 6 does differ between PH94B and placebo.

The estimand for the primary efficacy endpoint has the following components:

Table 4: Primary Efficacy Estimand

Attribute	Definition
Treatment	The treatment of interest is PH94B, 3.2 µg administered as an intranasal solution [REDACTED]. The active drug will be compared to a placebo control.
Population	The population of interest is adults with AjDA as defined by inclusion and exclusion criteria.
Variable of Interest	The variable of interest is change in subject reported severity of anxiety as measured by change from baseline in HAM-A total score using the SIGH-A, after 4 weeks of randomized treatment with study drug.
Intercurrent Events	Treatment discontinuation prior to the planned assessment time frame. Intercurrent events will be treated as described in Table 3.
Population Summary	The difference in change from baseline in mean HAM-A total score between PH94B-treated and placebo-treated subjects after 4 weeks of treatment.

Descriptive summaries of HAM-A total scores and change from baseline in HAM-A total scores will be provided for the primary endpoint by visit and by treatment group, based on the observed data.

An ANCOVA model with change from baseline to Visit 6 in HAM-A total scores as the outcome, treatment group as the factor, and baseline HAM-A as a covariate will be used to test the null hypothesis that there is no difference between PH94B- and placebo-treated subjects in mean change from baseline to Visit 6 in HAM-A total score. The analysis will be performed in the ITT population using SAS PROC MIXED. The following parameters will be presented: the change from baseline LS means and standard error (SE), 95% CI for the LS means, *p* value for testing if the LS mean is different than 0, LS mean difference between treatment groups (PH94B minus placebo) with SE, 95% CI for the LS mean difference, and *p* value for testing if the treatment LS means are equal.

If, for unanticipated reasons (intercurrent events), the fraction of subjects with missing change

AD-ST-33.06 Effective date: 12-Nov-2020

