Note: Subjects are summarized by planned treatment. The HAM-A is a questionnaire used to assess anxiety and is completed by trained personnel. It consists of 14 items, each scored on a 5-point scale rating anxiety from "Not Present" to "Very severe". The HAM-A total score is the sum of the individual item scores. Baseline is defined as the HAM-A total score from Visit 2 (Baseline). Change from baseline is calculated as result – baseline result. Least squares mean, LS mean differences (treatment – placebo), 95% CIs, and P values were obtained from an ANCOVA model with change from baseline to Visit 6 in HAM-A total scores as the outcome, treatment group as a factor, and baseline HAM-A total score as a covariate.

[1] Visit 6 (End of Treatment/Early Termination) includes data from subjects who either completed Visit 6 (End of Treatment) or who discontinued from the study and completed an early termination visit.

Reference Listing: 16.2.6.1

Programming Note: If the rate of missingness in change from baseline to Visit 6 HAM-A total scores is >0.05 for the ITT population, then report the results of the multiple imputation analysis. Rate of missingness is computed as the number of ITT subjects missing change from baseline to Visit 6 HAM-A total scores divided by the total number of subjects in the ITT population. If reporting the results of the multiple imputation analysis, add the following text to the footnote before the sentence beginning with "Least squares mean...": "Multiple imputation was performed using conditional specification with baseline HAM-A total score, sex, age, LSAS total score, and analysis site. Twenty-five imputation datasets were created." If the rate of missingness in change from baseline to Visit 6 HAM-A total scores is <=0.05 but greater than 0, then add the following text to the footnote: "Missing change from baseline in HAM-A total scores were imputed with treatment group mean change scores."

AD-ST-33.06 Effective date: 12-Nov-2020

Table 14.2.1.1 (cont.)
ANCOVA Change from Baseline in HAM-A Total Scores by Visit – Primary Analysis
ITT Population

Study Visit [1] Statistic	PH94B (N=XX)		Placebo (N=XX)	
	Observed	CFB	Observed	CFB
Visit 3				
n	XX	XX	XX	XX
Mean (SD)	XX.X (XX.XX)	XX.X (XX.XX)	XX.X (XX.XX)	XX.X (XX.XX)
Median	XX.X	XX.X	XX.X	XX.X
Min, Max	(XX, XX)	(XX, XX)	(XX, XX)	(XX, XX)
Visit 4				
n	XX	XX	XX	XX
Mean (SD)	XX.X (XX.XX)	XX.X (XX.XX)	XX.X (XX.XX)	XX.X (XX.XX)
Median	XX.X	XX.X	XX.X	XX.X

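### For subjects who stop treatment early, the plan lets both early and off-drug Week 4 HAM-A scores enter the primary analysis as Visit 6, matching neither the while-on-treatment strategy nor the 4-week variable

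*Protocol*

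**What the plan says.** Protocol 8.3 gives discontinuers two routes in order of preference. First: "Subjects who discontinue early from the study will be asked to return for originally scheduled weekly assessments". If that is not possible, "all attempts will be made to have subjects return to the study center to complete the assessments listed for Visit 6", as soon as they can. The same section adds that, where possible and reasonable, "the evaluations that were to be conducted at the completion of the study should be performed at the time of premature discontinuation". It also says "No tapering of IP is required in the event of early withdrawal", so weekly visits after stopping are off drug.

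Protocol Table 13-1 and SAP Table 3 (in SAP 6.1.4) name a while-on-treatment strategy for treatment discontinuation, aimed at response during active use of the product. They describe one route only: "Subjects who discontinue will undergo an Early Termination Visit and provide all Visit 6 outcome measures and safety assessments for the efficacy analysis". SAP 3.2 likewise calls this visit a Visit 6 (Early Termination) visit and does not mention weekly return.

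SAP 6.1.5 assigns visits as follows: "Efficacy data will not be windowed and will be analyzed as per the nominal visit present in the database". The footnote to the primary table shell, Table 14.2.1.1, says that Visit 6 "includes data from subjects who either completed Visit 6 (End of Treatment) or who discontinued from the study and completed an early termination visit". SAP Table 4 defines the primary variable as change in HAM-A "after 4 weeks of randomized treatment with study drug".

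**The concern.** The estimand names one strategy and one time point, but the rules that pick a discontinuer's score guarantee neither. One subject who stops may contribute a score taken before Week 4. Another who stops on the same day may contribute a score taken at Week 4 after weeks without drug. Both would be called Visit 6 and enter the ANCOVA as ordinary observed values.

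At stake is what the primary difference means once some subjects discontinue. It would be partly a response on treatment and partly a response regardless of treatment, in proportions set by which route each subject or site followed. SAP 8.2 carries the same Visit 6 and the same intercurrent events into the secondary endpoints, so they share the ambiguity.

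**Working it through.** No figure in the plan needs reproducing; this is a check of one rule against another.

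**Step 1: follow one subject.** Suppose a subject stops at Week 1.
- *Continued weekly attendance (Protocol 8.3, first choice).* The Visit 6 HAM-A is taken at Week 4, about 4 − 1 = 3 weeks after stopping. Protocol 7.1 treats a single week off drug before Visit 7 as a washout, so this cannot be an on-treatment value.
- *Early Termination (Protocol 8.3 fallback; Table 13-1; SAP 3.2; SAP Table 3).* The HAM-A is taken soon after Week 1, about 3 weeks before the time point in SAP Table 4.
- *Both.* Protocol 8.3 also asks for end-of-study evaluations at discontinuation, so the subject could have an early score and a Week 4 score. I found no rule for choosing between them.

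**Step 2: compare each score with the two definitions.**

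| Source of Visit 6 score | While on treatment (Table 13-1, SAP Table 3) | Week 4 treatment variable (SAP Table 4) |
|---|---|---|
| Completer on drug at Week 4 | Fits | Fits |
| Early Termination before Week 4 | Fits only if close to the last dose; no limit is stated | Does not fit |
| Week 4 visit off drug | Does not fit | Right week, but not 4 weeks of drug |

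**Step 3: look for a rule that removes the mismatched scores.**
- SAP 6.1.4 sets the Visit 6 HAM-A to missing for loss to follow-up, inability to complete the assessments, or prohibited medication. Being off drug and being early are not on the list.
- The case-by-case review in SAP 6.1.5 covers visits later than the 2-day window. It does not reach early visits, or off-drug visits attended on schedule.
- SAP 11, on changes from the planned analysis, does not address the point.

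**Step 4: ask whether a planned sensitivity analysis would show it.** The multiple-imputation trigger is a missing fraction above 0.05. With 40 subjects in the ITT set, 0.05 × 40 = 2. If three discontinuers each supply an early or off-drug Visit 6 score and nobody else is missing, the fraction is 0/40 = 0. No imputation is done, and neither sensitivity analysis runs, because SAP 8.1.1.1 and 8.1.1.2 make both conditional on imputation. Were those three scores treated as missing, the fraction would be 3/40 = 0.075 and multiple imputation and both sensitivity analyses would follow. Even when they run, both act only on missing values.

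**Step 5: size.** The readable text gives no dropout rate, effect size or SD, and Protocol 13.2 is redacted. The only scale available is the allocation: 40 subjects randomized 1:1 gives 20 per arm, so each subject carries 1/20 = 5% of a raw arm mean.

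**The case against.** The best defence is that every analysis passage describes a single route. Protocol Table 13-1, SAP 3.2 and SAP Table 3 all send discontinuers to Early Termination, and the primary table footnote presents completion and early termination as alternatives. Only the operational text of Protocol 8.3 mentions weekly return. The schedule of events is not readable, and SAP 1 says the data collection documents were still in development, so off-drug visits may carry their own label in the eCRF. Early scores are what while-on-treatment intends for early discontinuers. Listing 16.2.6.1 shows the date of each HAM-A, SAP 8.3 analyses Visits 3 to 5 separately, and the SAP calls the study exploratory.

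Much of this stands. The mixture is permitted, not certain; whether a subject would have two Visit 6 records depends on forms that cannot be seen; and only discontinuers are affected.

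It does not remove the point. SAP 1 leaves the timing and collection of assessments to the protocol, so the SAP cannot simply be read as overriding Protocol 8.3. If every site used the Early Termination route alone, early scores would still not match the SAP Table 4 variable. That fallback visit is only as soon as possible after stopping, so it is not certain to be on treatment either. Dates in a listing let a reader find the mixture afterwards; they do not change what enters the model.

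**Conclusion.** The point holds for discontinuers. Followed as written, the plan can put off-drug scores into an analysis declared to be while on treatment, and early scores into a variable defined at 4 weeks of treatment, with no planned analysis that separates them. This is a mismatch between the declared estimand and the data rule, not a preference for another estimand.

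Two stronger readings should be resisted. A reader might infer that the primary endpoint as a whole delivers neither definition. It does not fail for completers on drug at Week 4, who meet both.

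A reader might also try to size a bias. Assume improvement of 1 to 2.5 points per week and a stop at Week 1: the gap is 3 × 1 to 3 × 2.5 = 3 to 7.5 points. With an assumed excess of 2 to 4 discontinuers among 20 in one arm, the shift is 2/20 × 3 = 0.3 to 4/20 × 7.5 = 1.5 points. The documents do not support using that figure. Neither the slope nor the imbalance appears in them. It also measures the gap between early and Week 4 scores, which while-on-treatment keeps by design, and not the effect of mixing in off-drug scores. Size and direction remain unknown.

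**What to change.** Reconcile Protocol 8.3 with Table 13-1 and SAP 3.2, so that one description governs which visits a discontinuer attends. Then, in the SAP and before unblinding:

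- Keep the declared strategy. Define a discontinuer's analysis value as the last HAM-A on or before the recorded date treatment stopped, or the Early Termination HAM-A if it falls within a stated number of days of that date. Weekly HAM-A at Visits 3 to 5 makes this workable for most discontinuers. Say how a subject with no post-baseline score in that range is handled.
- Confirm that the eCRF captures the date treatment stopped. Protocol 8.3 records a discontinuation date for withdrawn subjects, which may not be the last dose, and Listing 16.2.5.2 shows only the first dose.
- Label off-drug weekly visits separately, so that they do not enter the primary analysis as Visit 6.
- Reword the SAP Table 4 variable to *at end of randomized treatment (Week 4 or last on-treatment assessment)*.
- Add a supplementary treatment-policy analysis using the scheduled Week 4 HAM-A where collected, and tabulate Visit 6 scores by source and arm.

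The cost is one derivation, one extra table and some rewording, plus a check that the stop date is captured. The real concession is that the primary variable is no longer strictly a Week 4 value.
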